10.2 Interstitial Photodynamic Therapy (I-PDT)

10.2.1 Porfimer Sodium Administration

Subjects will receive a single intravenous dose of porfimer sodium that will be administered approximately 48 ± 8 hours before the first I-PDT treatment.

Drug administration will take place in a room that has covered windows to protect the subjects from light exposure that can induce phototoxicity (i.e., direct sun light or visible artificial light that is more than 60 W). The Principal Investigator or designee will inject the subjects with porfimer sodium for this study.

A dose of 2 mg/kg of porfimer sodium will be administered by slow intravenous injection into a vein (3-5 minutes). Light-avoidance measures for approximately 30-90 days will be required. The Clinical Research Coordinator and staff nurses will explain the light-avoidance measures to each subject and written instructions will be handed out to the subjects (**Appendix F**). The subject will be cautioned to protect the site of the infusion from excessive direct sunlight and certain bright lights for up to 3 months. The site may be exposed to normal ambient light.

Vital signs will be done immediately after the end of the injection and 15 minutes after.

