10.2.2 Pre-treatment Planning

For all participants receiving I-PDT, a standard diagnostic head and neck scan with CT or MRI, will be obtained within 4 weeks prior to I-PDT. This imaging will be used for pre-treatment planning that will be conducted at [name] laboratory at Roswell Park, with the treating physician at each participating site.

The pretreatment planning will be carried out by following these steps:

- 1. If possible, clinically approved surface fiducial markers (using removal stickers) will be affixed to the skin (at the region of the tumor) prior to CT or MRI, to assist in the guidance of laser fibers, as described in Oakley et al. 2017(40).
- 2. The scans will be de-identified, linked to a subject ID, and copied on CD or transferred via secure network to [name] laboratory, 5-14 business days prior to the scheduled I-PDT.
- 3. The treating physician will use the CT or MRI scans and the image reconstruction model for defining the clinical target volume (CTV).
- 4. Image analysis software will be used to reconstruct the CT or MRI scans to generate a computer model of tumors and adjacent anatomy as we described in Oakley et al. 2015 and Oakley et al. 2017.(40, 41)
- 5. The treating physician will also use the computer model to recommend the number and location of closed-end transparent catheters that can be safely placed within the CTV.

- 6. The computer model (of the CTV) will be imported into a finite element modeling (FEM) software, to calculate the light intensity (mW/cm) and energy (J/cm) that will be required to be delivered by each fiber, so that 100% of the CTV receives the target light dose (i.e. computed fluence rate >8.6 mW/cm² and fluence >45 J/cm²) as much as possible.
- 7. The FEM simulations will be presented to the treating physician for approval of the treatment plan at least 5 business days prior to the I-PDT.

Note: If subjects are scheduled to receive additional I-PDT courses (at least 30 days from the previous I-PDT, see Section 10.4), per the physician's discretion, pre-treatment planning procedures for additional I-PDT courses are per the physician's discretion.

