10.3 Definition of Dose-Limiting Toxicity

Dose Limiting Toxicities will include:

Any adverse events (AEs) that are \geq grade 4 that are possibly, probably, or definitely related to the I-PDT, by recording the occurrence of AE during the first 30 days post final I-PDT treatment using the revised the National Cancer Institute (NCI) Common Terminology Criteria for Adverse Events version 5.0 (CTCAE v5.0). Dose Limiting Toxicities will be evaluated for 30 days post final I-PDT day.

If participants experience DLTs, further I-PDT sessions will be held until DLT resolution as well as after porfimer sodium clearance.

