10.4 Dose Escalation/Finding Schema

The FDA approved porfimer sodium dose (2 mg/kg) will not change. We will aim to deliver light fluence rate of ≥ 8.6 mW/cm² and fluence of ≥ 45 J/cm² to 100% of the CTV (dose level 1), as much as possible. Dose level -1 will ≥ 5.0 mW/cm² and fluence of ≥ 45 J/cm² to 100% of the CTV.

Table 2. The study plan for finding optimal fluence rate in I-PDT with Photofrin in patients with LAHNC.			
Dose Level Number of patients with DLT at a given dose level		Decision rules	
Dose Level 1 (Starting): The maximum fluence rate, scaled for	0 out of 3	Enter 3 patients at Dose Level 1 : The laser fluence rate and fluence, scaled for human, which induced maximum photoreaction in the animal models	
human, which induced effective	1 out of 3	Enter 3 more patients at this Dose Level .	

photoreaction in the animal models.	≥2	Enter 3 patients at Dose Level -1 : The laser fluence rate and fluence, scaled for human, which induced minimal toxicity in the animal models.
	≤ 1 out of 6	This is generally the recommended Phase II dose rate/dose. At least 6 patients must be entered at the recommended Phase II dose.

In participants where their tumors may require more than one course of I-PDT for complete effective illumination of the CTV, up to three sessions of I-PDT may be performed, at the discretion of the treating physician. The FDA approves to administer up to three courses of PDT with Photofrin® each separated by at least 30 days in the treatment of esophageal and endobronchial cancer (http://www.photofrin.com/wp-content/uploads/2013/02/prescribing-info.pdf.). Therefore, treatment sessions in this study will be conducted at least 30-days apart. The porfimer sodium dose (2 mg/kg) will remain the same.

See Appendix D 1 for the Dose Escalation Schedule of Events. The date of the last I-PDT course will be used to determine the scheduling of the follow up SoC related to this study.

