11.2 Baseline Evaluations

The following will be performed within 8 weeks prior to administration of porfimer sodium:

- Informed consent: Must be completed prior to receiving any study-related procedures
- Medical history
- Physical examination including vital signs (i.e., temperature, heart rate, respiratory rate, blood pressure, body weight, height, and pain assessment using a verbal score of 0 10) *
- Hematology (i.e., complete blood count (CBC) with auto differential, absolute neutrophil count (ANC), and platelets) *, **
- Chemistry (i.e., AST, ALT, total bilirubin, alkaline phosphatase, creatinine, potassium, glucose, and calcium) *
- Pregnancy test (urine) in females of childbearing potential **
- ECOG Performance Status **
- UW OoLO v4 #
- Standard imaging for patients with HNC (i.e., CT and/or MRI) *, at least 10 business days prior to the scheduled I-PDT #
- Pretreatment planning #
- Concomitant Medications (including narcotic and nonnarcotic analgesics) **

**These will be done prior to later 2nd and 3rd later I-PDT sessions (if later I-PDT sessions are required per treating physician's discretion per Section 10.4). Height does not need to be reassessed for later possible I-PDT sessions. If later I-PDT courses are deemed necessary, previous study treatment adverse events will be reviewed before the start of next I-PDT course.

Performed as per PI discretion if 2nd and 3rd I-PDT courses are deemed necessary as per Section 10.4.

^{*}These are standard of care and may be used for baseline evaluation if performed before informed consent but within 4 weeks of porfimer sodium and can be used for the pretreatment planning.

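### After a dose-limiting toxicity the plan sets only a hold, with no mandatory stop or light reduction, and closing a light level redirects only new entrants

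*Combined protocol and SAP*

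**What the plan says.** Section 10.3 defines a DLT as an event of grade 4 or higher that is at least possibly related to I-PDT, assessed to 30 days after the final I-PDT day. For the participant who has one, it gives a single consequence: "further I-PDT sessions will be held until DLT resolution as well as after porfimer sodium clearance".

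Section 10.4 allows repeat treatment: "up to three sessions of I-PDT may be performed, at the discretion of the treating physician". Courses are at least 30 days apart, and the drug dose stays at 2 mg/kg. No rule is given for the light level of a later course. The actions in Table 2 of that section all concern entry. With no DLT in three, the action is "Enter 3 patients at Dose Level 1"; with one in three, three more enter at the same level; with two or more, the next three enter at Level -1. The lower level is defined by minimums: "Dose level -1 will ≥ 5.0 mW/cm² and fluence of ≥ 45 J/cm² to 100% of the CTV".

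Section 10.2.2 step 6 has one planning target for everyone, that the whole target volume "receives the target light dose (i.e. computed fluence rate >8.6 mW/cm² and fluence >45 J/cm²) as much as possible". Its closing note adds that "pre-treatment planning procedures for additional I-PDT courses are per the physician's discretion".

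Appendix D also allows light without new drug. Note 16 lets a course be split, with further sessions within 14 days. Note 17 allows one or two more light-only treatments within 2 to 3 weeks of the drug. Appendix D 1 note P repeats the split-session rule for later courses.

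On safeguards, section 11.2 says that "previous study treatment adverse events will be reviewed before the start of next I-PDT course". Section 10.5 lists treatment-related toxicity as a discontinuation reason and lets the investigator withdraw a subject. Sections 19.7 and 20.0 provide committee oversight.

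**The concern.** Irradiance is the variable this trial exists to set, and the design's own response to toxicity is less light. That response reaches the next patients but not the patient who had the event. It also does not reach a patient with courses outstanding when Level 1 closes. The DLT threshold is already high, and section 19.7 singles out life-threatening bleeding and emergency airway events. A participant who survives such an event can resume under a stated rule at the irradiance that preceded it. Another could be illuminated at a level the trial has just judged too toxic.

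**Working it through.** **Plan's own figure.** Two light levels × up to 6 patients = 12, the same as four cohorts of 3. The stated maximum of 12 reproduces, and nothing below changes it.

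**Which text sets the light level of a later illumination?**

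| Situation | Text that applies | Light level set? |
|---|---|---|
| Participant with a resolved DLT | 10.3: hold until resolution and clearance | No |
| Participant mid-course when Level 1 closes | Table 2: next three enter at Level -1 | No; entrants only |
| Any later course | 10.4: drug dose unchanged | No |
| Planning target | 10.2.2 step 6: above 8.6 mW/cm² | Yes, but not by assigned level |
| Participant moved to Level -1 | 10.4: at least 5.0 mW/cm² | Floor only; 8.6 also satisfies it |

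**Do the safeguards fill the gap?** The review in 11.2 (and Appendix D 1 note Oi) has no go/no-go criterion. Section 10.5 is permissive. Section 12.0 adds withdrawal when I-PDT cannot be given or the patient loses hemodynamic stability during it; a DLT is not listed. Section 19.3 halts accrual for excess serious events, which does not govern re-treatment. Appendix D 1 note N takes patients off treatment 30 days after the last I-PDT, but a further course moves that date.

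**How often could it arise?** The documents give no DLT rate, so p below is an assumed per-participant rate over all courses. Table 2 takes Level 1 to six patients unless two or more of the first three have a DLT.

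- At least one DLT at Level 1: 1 − (1−p)⁶
- Level 1 closes: 1 − (1−p)⁶ − 6p(1−p)⁵
- Expected Level 1 participants with a DLT: 3p + 3p[(1−p)³ + 3p(1−p)²]

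At p = 0.20 these are 1 − 0.262 = 0.738; 0.738 − 0.393 = 0.345; and 0.6 + 0.6 × 0.896 = 1.14.

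| Assumed p | At least one DLT | Level 1 closes | Expected participants with a DLT |
|---|---|---|---|
| 0.10 | 46.9% | 11.4% | 0.59 |
| 0.20 | 73.8% | 34.5% | 1.14 |
| 0.30 | 88.2% | 58.0% | 1.61 |

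The last column is a ceiling on the number who could be re-treated after a Level 1 DLT. It includes fatal events and participants with no further course planned.

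**Others mid-course at closure (illustrative).** Twelve participants in 60 months (section 7.0) is one per 5 months, about 150 days. Three courses span at least 2 × 30 = 60 days (10.4) or 2 × 42 = 84 days (Appendix D, six-week gaps). Adding the 30-day window gives at least 90 or 114 days. With evenly spaced entry and minimum gaps, nobody else is then in treatment when a DLT closes the level. Overlap begins once gaps average more than (150 − 30)/2 = 60 days, or if entries bunch. Both spans are minimums, so this gives scale only.

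**What the hold adds.** Section 10.3 does not define clearance. The nearest guide is in 10.2.1, "Light-avoidance measures for approximately 30-90 days will be required", which is a skin precaution and not a clearance criterion. As an illustrative minimum, drug is given 2 days before light, so 30 days after injection is day 28 after light. That lies inside the ordinary 30-day gap between full courses, so at its shortest the clearance condition adds no delay to a next full course. It does block the 14-day split sessions and the 2-to-3-week light-only treatments for the participant with the DLT, because note 16 expects drug in the tumor for at least 30 days. Those early sessions are therefore a gap only for other participants when a level closes.

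**The case against.** The plan does address the participant with a DLT, and a hold may be a deliberate choice. Later courses exist to complete illumination of the target volume, and split sessions light other parts of the tumor, so a further illumination need not hit the tissue that reacted. These patients are not amenable to curative treatment, and whether to continue is a benefit-risk judgment. Adverse events are reviewed before each course, the investigator and sponsor can stop treatment, and the monitoring committee can recommend suspension.

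Much of this stands. A reader might infer that the plan has no way to stop treatment after a DLT. It has several; what it lacks is a mandatory stop. A reader might also infer that it directs same-light re-treatment, or continued treatment at a closed level. No sentence does so: the first follows from a hold with no light condition, the second from silence. Nor are DLTs on later courses lost, because the window runs from the final I-PDT day. The percentages above are chances of a DLT or of closure, not of re-treatment.

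What the objection does not supply is a light level. Discretion over whether to continue leaves open at what irradiance, and the only written planning target is the higher one.

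**Conclusion.** The point holds as a gap in a stated rule: the text permits, but does not require, same-irradiance re-treatment of a grade 4 DLT survivor and illumination at a level just closed. Exposure is probably about one participant, with up to two further courses. That rests on assumed DLT rates of 10% to 30% and roughly even accrual over 5 years. The documents do not say how many participants will be offered a further course, so no re-treatment probability can be given. No figure in the plan is wrong and the sample size is unaffected. It should be fixed because the potential harm is serious and the remedy is a few sentences.

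**What to change.** 1. **Section 10.3.** A participant with a DLT at Level 1 receives no further I-PDT, or continues only at Level -1 after resolution, drug clearance and review by the existing Early Phase Clinical Trials Committee. A participant with a DLT at Level -1 stops.
2. **Section 10.4.** When a second DLT closes a level, hold all pending courses, split sessions and light-only treatments at that level, and make Appendix D notes 16 and 17 and Appendix D 1 note P subject to this. If Level 1 closed, they proceed only at Level -1 after committee review. If Level -1 closed, they stop.
3. **Light targets.** Define the Level -1 planning target as at least 5.0 and below 8.6 mW/cm², as far as the plan allows, and make 10.2.2 step 6 refer to the assigned level. Without a ceiling, a move to Level -1 guarantees no reduction.
4. **Counting.** Participants moved down stay in the Level 1 count and do not enter the Level -1 denominator. Their later events go to the committee separately.

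The cost is a short amendment and an occasional case for a committee that already meets regularly. The maximum remains 12. The real downside is that a few participants may have a later course delayed, reduced or forgone.

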10.4 Dose Escalation/Finding Schema

The FDA approved porfimer sodium dose (2 mg/kg) will not change. We will aim to deliver light fluence rate of ≥ 8.6 mW/cm² and fluence of ≥ 45 J/cm² to 100% of the CTV (dose level 1), as much as possible. Dose level -1 will ≥ 5.0 mW/cm² and fluence of ≥ 45 J/cm² to 100% of the CTV.

Table 2. The study plan for finding optimal fluence rate in I-PDT with Photofrin in patients with LAHNC.			
Dose Level Number of patients with DLT at a given dose level		Decision rules	
Dose Level 1 (Starting): The maximum fluence rate, scaled for	0 out of 3	Enter 3 patients at Dose Level 1 : The laser fluence rate and fluence, scaled for human, which induced maximum photoreaction in the animal models	
human, which induced effective	1 out of 3	Enter 3 more patients at this Dose Level .	

photoreaction in the animal models.	≥2	Enter 3 patients at Dose Level -1 : The laser fluence rate and fluence, scaled for human, which induced minimal toxicity in the animal models.
	≤ 1 out of 6	This is generally the recommended Phase II dose rate/dose. At least 6 patients must be entered at the recommended Phase II dose.

In participants where their tumors may require more than one course of I-PDT for complete effective illumination of the CTV, up to three sessions of I-PDT may be performed, at the discretion of the treating physician. The FDA approves to administer up to three courses of PDT with Photofrin® each separated by at least 30 days in the treatment of esophageal and endobronchial cancer (http://www.photofrin.com/wp-content/uploads/2013/02/prescribing-info.pdf.). Therefore, treatment sessions in this study will be conducted at least 30-days apart. The porfimer sodium dose (2 mg/kg) will remain the same.

See Appendix D 1 for the Dose Escalation Schedule of Events. The date of the last I-PDT course will be used to determine the scheduling of the follow up SoC related to this study.

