In previous publications we demonstrated that FEM could be used to plan and guide interstitial light delivery in models mimicking human tumors (40, 41). This modeling was used in a recent paper to guide I-PDT in the treatment of mice and NZW rabbits with VX2, part of the results are shown in figures 1 and 2 above. ([name] et al. Journal British of Cancer, Accepted for publication July 5, 2018).

We therefore propose to use the treatment planning to administer intratumoral 630 ± 3 nm laser light at >8.6 mW/cm2 and >45 J/cm2 to 100% of the tumor volume, as described in details in Section 10.2.

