10.2.3 I-PDT Procedure

The I-PDT will commence by following these steps:

- 1. An ultrasound system will be used, prior to fiber insertion, to confirm that the close-end sterile catheters can be safely placed into the CTV, according to the approved treatment plan. These catheters will be used to accommodate cylindrical laser fibers that will deliver the therapeutic light. If possible, an intraoperative CT (or other clinically approved radiological imaging) will be used to image the actual location of the inserted catheters.
- 2. Laser fibers with cylindrical end will be inserted into the close-end sterile catheters, according to the approved treatment plan. Only one laser fiber will be inserted into each catheter.
- 3. Additionally, dosimetry fibers to measure light will be inserted into other, nearby, close-end sterile catheters to monitor the light delivery.
- 4. The laser system(s) will be turned on to deliver the therapeutic light (630 ± 3 nm) into the tumor.
- 5. A light dosimetry system (described in Section 32.2) will be used to monitor the light fluence rate, fluence and tumor during I-PDT, in all participating sites.

The laser treatment and dosimetry fibers could be moved from one close-end sterile catheter to another to deliver the planned light fluence rate and fluence, and monitor the light and thermal dose. At any given time, there will be only one fiber (treatment or dosimetry) in a close-end sterile catheter. The laser fibers and detectors will not be in direct contact with patient tissue. Following administration of the laser light, the laser fibers and detectors will be removed, they will be cleaned and disinfected with an acceptable method (e.g., Cidex). The fibers and detectors can be reused, as they must be checked for calibration prior to each procedure.

Light Exposure Precautions

Light precautions will be maintained from the moment the subject enters the hospital and will continue while the subject is in the surgical suite and on the surgical subject care units.

Subjects are instructed to wear their protective eyewear when they travel to the hospital. The surgery will be performed with room lights, which are modified by amber filters to minimize unwanted activation of the photosensitizing drug and inadvertent light exposure to the subjects. Yellow filter paper will be employed over the procedure room lights and the surgeons' headlights

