19.6 Adverse Events

The frequency of toxicities will be tabulated by grade across all dose levels and cycles. All subjects who receive any study treatment will be considered evaluable for toxicity.

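### The planning rule names only the Level 1 light target and Level -1 is set only as a floor, so the intended step down from 8.6 to 5.0 mW/cm² is not secured

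*Combined protocol and SAP*

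**What the plan says.** Porfimer sodium is fixed at 2 mg/kg, and both levels share the same fluence floor, so the fluence-rate target is what separates them.

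- Section 10.4, Level 1: "We will aim to deliver light fluence rate of ≥ 8.6 mW/cm² and fluence of ≥ 45 J/cm² to 100% of the CTV", qualified as far as this is possible.
- Section 10.4, Level -1: "Dose level -1 will ≥ 5.0 mW/cm² and fluence of ≥ 45 J/cm² to 100% of the CTV". Table 2 sends patients there after 2 or more DLTs and describes it as the light "which induced minimal toxicity in the animal models". Section 10.3 defines a DLT as a grade 4 or higher event at least possibly related to I-PDT.
- Section 10.2.2 (planning) opens with "For all participants receiving I-PDT, a standard diagnostic head and neck scan with CT or MRI, will be obtained" and says that this imaging is used for planning. Step 6 then has the finite element software work out each fibre's output "so that 100% of the CTV receives the target light dose (i.e. computed fluence rate >8.6 mW/cm² and fluence >45 J/cm²". No step mentions the dose level.
- Section 2.4 states the same single target: "We therefore propose to use the treatment planning to administer intratumoral 630 ± 3 nm laser light at >8.6 mW/cm2 and >45 J/cm2".
- Section 10.2.3 lets fibres be moved between catheters "to deliver the planned light fluence rate and fluence".
- Section 19.6: "The frequency of toxicities will be tabulated by grade across all dose levels and cycles". No table by level is specified. Section 19.8 records delivered fluence and fluence rate at each detector location.

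**The concern.** The section that turns a dose level into fibre settings holds one number, the starting level's. The section that defines the lower level gives a minimum and no upper limit. Neither forces the other to change when a patient is assigned to Level -1.

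Level -1 is the only de-escalation step, and it opens only after at least two patients have had a related event of grade 4 or worse. The protection of the next patients rests on the planning target actually falling. A primary objective is also to recommend an irradiance for Phase 2. If the planned light does not differ between levels, a Level -1 recommendation would carry a label that does not match what was given. A toxicity summary pooled over two irradiances would not show the adverse-event profile of the one recommended.

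**Working it through.** **1. The plan's own figure.** Two levels × 6 patients = 12, and four cohorts × 3 = 12. This matches the stated maximum in Sections 4.0 and 19.1. Nothing below changes it.

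**2. The texts side by side.**

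| Section | Applies to | Planned fluence rate | Depends on level? |
|---|---|---|---|
| 2.4 | Study proposal | >8.6 mW/cm² | No |
| 10.2.2, step 6 | Planning section for all I-PDT participants | >8.6 mW/cm² | No |
| 10.4, Level 1 | Starting level | ≥8.6 mW/cm² | Yes |
| 10.4, Level -1 | After ≥2 DLTs | ≥5.0 mW/cm² | Yes |

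The value 5.0 appears only in 10.4.

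**3. Nesting.** Let m be the planned minimum fluence rate in the CTV. Step 6 requires m > 8.6; Level -1 requires m ≥ 5.0. Any m > 8.6 satisfies both.

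- Intended reduction: 1 − 5.0/8.6 = 0.419, or 42%.
- Reduction compelled by the text: 0%.
- A plan with its minimum at 8.6 sits 8.6/5.0 − 1 = 0.72, or 72%, above the Level -1 floor.
- If fluence rate scales with fibre output for a fixed tumour and fibre layout (assumption), a 5.0 target needs 5.0/8.6 = 58% of the Level 1 output.

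**4. How often this could matter.** The documents give no DLT rate, so p is assumed. Table 2 adds three patients at Level 1 after either 0/3 or 1/3, so P(Level -1 opens) = P(X ≥ 2), X ~ Bin(6, p). Suppose Level -1 patients are planned at the Level 1 target, p is unchanged, and Level -1 is judged by the same rule of at most 1 DLT in 6. Then P(Level -1 passes) = P(X ≤ 1).

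| Assumed p | Level -1 opens | Level -1 passes | Both |
|---|---|---|---|
| 0.10 | 0.114 | 0.886 | 0.101 |
| 0.20 | 0.345 | 0.655 | 0.226 |
| 0.25 | 0.466 | 0.534 | 0.249 |
| 0.33 | 0.642 | 0.358 | 0.230 |
| 0.50 | 0.891 | 0.109 | 0.097 |

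Under those suppositions there is about a 10% to 25% chance of recommending Level -1 with no reduction in planned light. The table does not say how likely it is that a planner would use the wrong target; no figure in the documents bears on that.

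**5. Pooling, as an example.** With 2/6 affected at Level 1 (33%) and 0/6 at Level -1 (0%), a pooled table shows 2/12 = 17% (exact 95% CI 2% to 48%).

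**6. Illumination time at the floor.** For a point lit continuously at the minimum, time = fluence ÷ fluence rate. At 8.6 mW/cm²: 45/0.0086 = 5,233 s = 87 min. At 5.0 mW/cm²: 45/0.0050 = 9,000 s = 150 min. This is illustrative, because fibres may be moved. It measures a cost of the lower level, not a harm from the gap.

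**The case against.** Section 10.4 is the dose-finding section and gives Level -1 its own number. The figure in step 6 can be read as the starting level's value, with the later, more specific section controlling. The phrase about all participants attaches grammatically to the scan; carrying it over to the number in step 6 is a fair inference but is not stated. Section 2.4 is background and points to Section 10.2. The treating physician approves each plan, and the Early Phase Clinical Trials Committee and the DSMC monitor safety. A planner who solves for 5.0 will obtain lower fibre output than one who solves for 8.6.

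Much of this stands. A reader might infer that Level -1 patients will be treated at the Level 1 dose, or that the protocol contains no real lower level. The documents do not support either: a lower level is defined and its purpose is clear. What remains is that correct planning depends on departing from the only number in step 6, and no step asks for the plan to be checked against the assigned level.

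A reader might also infer that toxicity will be examined only in pooled form. That too goes beyond the text. Table 2 counts DLTs by level for the dose decision, and the wording of 19.6 can be read as covering each level. By-level numbers would also be weak evidence: 2/6 against 0/6 gives a two-sided Fisher p of 0.45, and 0/6 has an exact 95% upper limit of 46%. This half of the point is secondary and descriptive.

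Setting dose by a planned minimum is sound in I-PDT and is not criticised here.

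**Conclusion.** The point holds as a gap between the planning rule and the dose-level definition. Step 6 names one target, Level -1 is a floor that a Level 1 plan also meets, and following both sections to the letter compels none of the intended 42% reduction. That rests on the text and on no assumption about toxicity. The 10% to 25% figure is conditional on assumed DLT rates of 10% to 50%, unchanged planning at Level -1 and the same pass rule there; it shows the consequence of the error, not its likelihood. The plan should be corrected because the gap sits on the only safeguard used after severe related toxicity and bears on the irradiance objective. The reporting point is minor: an explicit by-level adverse-event table is missing, while the dose decision itself is already made by level.

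**What to change.** In Section 10.2.2, step 6, replace the single target with that of the patient's assigned level, and repeat it in 10.4:

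- Level 1: planned minimum CTV fluence rate ≥8.6 mW/cm².
- Level -1: planned to a minimum of 5.0 mW/cm², with a small tolerance above it that the sponsor states and that stays well below 8.6.
- Both levels: fluence ≥45 J/cm².

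A rule allowing anything under 8.6 at Level -1 would not be enough: a plan at 8.5 would comply and be only 1 − 8.5/8.6 = 1.2% below Level 1. Since the rule bounds the planned minimum, tissue near a fibre may still receive more.

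In Section 19.6, keep the overall table, add adverse events by dose level, and list them against the delivered fluence rate and fluence already recorded under 19.8.

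The cost is wording in two sections and an extra table and listing from data already collected. The downsides are slightly less planning freedom and longer illumination at Level -1, and very small numbers per level (about 6), so the by-level display is descriptive only.
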